9.4.6 PLANNED INTERIM ANALYSES

Additional details of the planned interim analyses will be provided in interim analysis plans, 1 plan each for Phase 2b and Phase 3, respectively.

Phase 2b: An interim efficacy analysis will be conducted when 120 participants have completed Day 8 assessments or Day of Discharge assessments if the participant is discharged prior to Day 8. To account for early recovery, deaths, and lab errors which may lead to lack of Day 8 D-dimer in approximately 20% of patients, 120 participants will provide for approximately 100 participants to be evaluated in the interim efficacy analysis. The interim efficacy analysis will test for futility based on the primary study hypothesis. Additionally, at the interim efficacy analysis, the Data Safety Monitoring Committee will be empowered to adjust sample size as pre-specified in the Phase 2b interim analysis plan. An interim safety analysis will occur after approximately one third of the total target enrollment (i.e., 30-40 participants) completes the Day 8 assessments. Outcomes of the interim analyses may include changes to dose regimens, or other adjustments related to safety or trial logistics. No spending of type 1 error will occur during the interim analysis.

Phase 3: Interim analyses on time to recovery will occur when approximately 33% and 67% of the initial target number of events (i.e., 120 and 240) have occurred. The following is an outline of the interim analysis plan:

- Both interim analyses will include a non-binding assessment for futility; no formal boundary will be used in the first interim analysis, while the second will use a boundary corresponding to 10% conditional power.
- Both interim analyses will have a specified boundary for unequivocal efficacy corresponding to a p-value of 0.0001, 1-sided solely for the purposes of a sample size re-estimation at the second interim analysis; the study will not be stopped for unequivocal efficacy even if this boundary is crossed at one of the interim analyses.
- The interim analysis at 67% of the initial target number of recovery events will include a "promising zone" analysis of conditional power, whereby sample size may be increased by up to 150 additional participants (e.g., 600 total participants) and 120 additional events (i.e., 480 total events) to target 90% conditional power for the final analysis if conditional power, based on the estimated interim HR, is within 30% and 80%.

In addition to the unblinded interim analyses described above, given that the Phase 3 is event-driven and participants are followed for the primary endpoint for a fixed period of time (30 days), the event rate will be monitored in a blinded fashion throughout the study. If the blinded (noncomparative) event rate indicates that less than 360 primary events are unlikely to be observed among 450 randomized participants – or the upsized number of events and participants based on the conditional power analysis

at the second interim analysis described above – the number of randomized participants will be increased to ensure the target number of events is achieved.

The alpha level for the final analysis will be 0.05 – 0.0001, or 0.0499.

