5.5 STRATEGIES FOR RECRUITMENT AND RETENTION

The target sample size for Phase 2b is approximately 160 participants, with an additional approximately 450 planned during Phase 3. Eligibility criteria are broad to facilitate enrollment, the primary requirement being elevated D-dimer. In published data, 68% of patients hospitalized with COVID-19 had D-dimer > 0.5 ng/mL.³²

Enrolled participants are anticipated to reflect the epidemiology of COVID-19. In May 2020, 46%, 30% and 24% of hospitalized patients with COVID-19 in the US were >65, 50-64 and <50 years of age, respectively. Race/ethnicity was reported as 37% Non-Hispanic White, 40% Non-Hispanic Black and 14% Hispanic. Concomitant medical conditions included hypertension 59%, CV disease 35%, metabolic disease 42%, obesity 50% and renal disease 16%.²⁹

We anticipate enrolling at approximately 20 sites in Phase 2b and 80 clinical sites in Phase 3, selected for experience providing high quality clinical trial data and for the prevalence and ability to recruit the target population. Sites will be selected in geographic areas with high rates of COVID-19 in the US and abroad. Because of the rapid timeline, regulatory approval and drug importation time will be considered during site selection.

Adherence is facilitated by planned administration of all study medication in-hospital. Retention should be facilitated due to the short duration of follow up and limited number of study-related activities. Follow up for clinical outcomes and AEs may be conducted remotely.

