9.2 SAMPLE SIZE DETERMINATION

During Phase 2b, approximately 160 participants will be enrolled and randomized 1:1:2 to rNAPc2 dose regimen 1, rNAPc2 dose regimen 2, and heparin standard of care, respectively. Assuming approximately 20% of participants may not be evaluable for any reason, 160 randomized participants will provide for approximately 130 evaluable participants. At a sample size of 160 or greater, the study will have adequate power across a range of effect sizes. This sample size was selected to ensure inferences for the primary endpoint analysis will be robust, given certain potential confounding factors such as missing data (random or non-random), heterogeneous application of heparin (low molecular weight and unfractionated; prophylactic and therapeutic), effects of subject-level covariates (e.g., comorbidities), and effects of site-level covariates (e.g., country).

		Power, Primary Endpoint					
		Effect Size (Proportional Reduction)					
		Enrolled Subjects	Evaluable Subjects	20%	25%	30%	35%
Sample Size	80	64	55.8%	67.4%	75.6%	81.0%	84.5%
	100	80	60.5%	72.7%	80.1%	84.9%	87.8%
	110	88	63.6%	76.2%	80.7%	86.6%	89.2%
	120	96	65.2%	78.0%	82.8%	86.9%	91.0%
	130	104	68.2%	79.3%	84.8%	88.7%	91.7%
	140	112	68.9%	80.7%	86.6%	89.3%	92.5%
	160	128	71.3%	83.1%	88.3%	91.3%	94.1%
	180	144	74.9%	84.5%	89.5%	92.5%	94.6%
	200	160	77.2%	86.5%	91.0%	93.8%	95.8%
*Significance via $\alpha = 0.05$							
†Simulated with 20% Missing Data							
‡Percentages as Averages Across Other Simulation Conditions							

During Phase 3, 450 patients yielding 360 recovery events randomized 1:1 into the two treatment groups have approximately 80% power with 5%, two-sided type 1 error assuming median recovery times of 11 and 15 days for the rNAPc2 and heparin groups, respectively (i.e., treatment hazard ratio (HR)=1.36). As described in [Section 9.4.6 Planned Interim Analyses](#), at the second Phase 3 interim analysis (67% of the initial target number of events), if conditional power, based on the estimated interim hazard ratio, falls within 30% and 80%, the sample size and target number of events will be increased to target 90% conditional power for the final analysis.

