2.2 Sample Size Determination

During Phase 2b, approximately 160 participants will be enrolled and randomized 1:1:2 to rNAPc2 dose regimen 1, rNAPc2 dose regimen 2, and heparin SoC, respectively. Assuming approximately 20% of participants may not be evaluable for any reason, 160 randomized participants will provide for approximately 130 evaluable participants. At a sample size of 160, the study will have adequate power across a range of clinically meaningful effect sizes, operationalized as proportional reductions in D-dimer (relative to heparin) from 20% to 40% in increments of 5% (see below). This sample size was selected, based on a statistical simulation using Wilcoxon rank sum and assuming a 20% missing/dropout rate, to ensure inferences for the primary endpoint analysis will be robust, given certain potential confounding factors such as missing data (random or non-random), heterogeneous application of heparin (low molecular weight and unfractionated; prophylactic and therapeutic), effects of subject-level covariates (e.g., comorbidities), and effects of site-level covariates (e.g., country).

Power, Primary Endpoint							
	Effect Size (Proportional Reduction)						
	Enrolled Subjects	Evaluable Subjects	20%	25%	30%	35%	40%
Sample Size	80	64	55.8%	67.4%	75.6%	81.0%	84.5%
	100	80	60.5%	72.7%	80.1%	84.9%	87.8%
	110	88	63.6%	76.2%	80.7%	86.6%	89.2%
	120	96	65.2%	78.0%	82.8%	86.9%	91.0%
	130	104	68.2%	79.3%	84.8%	88.7%	91.7%
	140	112	68.9%	80.7%	86.6%	89.3%	92.5%
	160	128	71.3%	83.1%	88.3%	91.3%	94.1%
	180	144	74.9%	84.5%	89.5%	92.5%	94.6%
	200	160	77.2%	86.5%	91.0%	93.8%	95.8%

*Significance via $\alpha = 0.05$
 †Simulated with 20% Missing Data
 ‡Percentages as Averages Across Other Simulation Conditions

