8.3 Laboratory Data

A summary of laboratory (Central Laboratory) values (e.g., AST, ALT and bilirubin) outside normal limits (i.e., either above the ULN or below the lower limit of normal (LLN) where limits are defined), as well as a summary of any participant potentially meeting the criteria for Hy's law will be provided where Hy's Law criteria will be defined as: AST or ALT > 3× ULN and total bilirubin > 2× ULN at any time during the study.

9 Interim Analyses

Additional details of these analyses will be described in the DSMC Charter.

10 Composite and Net Endpoints

Composite endpoints will first be analyzed as an aggregate and then component-wise, as discussed in the context of modeling clinical events in [Section 7.2.3](#). The primary approach to net outcomes will be to perform them in all randomized patients in the 30-day study period.

Composite/net clinical outcomes include the combination of irreversible harm and efficacy outcomes, including:

- All-cause mortality, thrombotic events, initiation of organ support, rehospitalization adjudicated as to its relatedness to COVID-19.

11 Subgroup and Sensitivity Analyses

The sensitivity analyses will be performed on the ITT, mITT, and Per Protocol populations.

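### Two triggers in Protocol 9.4.6 do not work as written: the Phase 2b safety look equates one third of 160 with 30–40, and the Phase 3 event-shortfall rule is inverted

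*Protocol*

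**What the plan says.** **Phase 2b safety look.** Protocol 9.4.6: "An interim safety analysis will occur after approximately one third of the total target enrollment (i.e., 30-40 participants) completes the Day 8 assessments". The enrolment target is given consistently elsewhere. Protocol 5.5 says "The target sample size for Phase 2b is approximately 160 participants", and SAP 2.2 says "approximately 160 participants will be enrolled and randomized 1:1:2"; the Protocol synopsis and Section 9.2 agree. Section 9.4.6 adds that "Outcomes of the interim analyses may include changes to dose regimens". SAP Section 9 on interim analyses says only "Additional details of these analyses will be described in the DSMC Charter".

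**Phase 3 event-rate rule.** At the end of Protocol 9.4.6, recovery events are monitored blind to treatment. The condition for action is that the pooled rate indicates that "less than 360 primary events are unlikely to be observed among 450 randomized participants". The action is that "the number of randomized participants will be increased to ensure the target number of events is achieved". The same sentence covers the larger target that applies if the second interim analysis increases the sample size. Protocol 9.2 sets 450 participants and 360 events, "assuming median recovery times of 11 and 15 days for the rNAPc2 and heparin groups".

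**The concern.** The safety-look sentence offers a fraction and a count as if they were the same number. With a target of 160 they are not, so the timing depends on which half the reader follows. It is one of the scheduled looks at which the full Data Safety Monitoring Committee reviews bleeding, serious adverse events and deaths (Protocol 10.1.5).

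In the Phase 3 rule the condition is a double negative pointing the wrong way. If a total below 360 is unlikely, the target is expected to be met, yet that is when the text adds participants. When a shortfall is expected, the condition is false and the text adds none. This rule protects the event target. The promising-zone increase at the second interim analysis depends on conditional power, not on the event count, so it does not replace it. Protocol 7.2 also dismisses replacement of participants because Phase 3 is event driven, which relies on the event target being met some other way.

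**Working it through.** **A. Safety look**

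Inputs: target 160 and allocation 1:1:2 (Protocol 9.2, SAP 2.2); about 130 evaluable, 128 in the power table (Protocol 9.2); trigger of one third, or 30–40 (Protocol 9.4.6).

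- One third of the target: 160/3 = 53.3.
- Stated count as a fraction: 30/160 = 18.75%; 40/160 = 25%.
- Gap: 53.3 − 40 = 13.3; 53.3 − 30 = 23.3.
- Evaluable participants as the denominator: 130/3 = 43.3 and 128/3 = 42.7, still above 40. The sentence in any case refers to total enrolment.
- Totals for which 30–40 would be one third: 3 × 30 = 90 to 3 × 40 = 120.
- Participants per rNAPc2 dose group (one quarter of those in the look): 30/4 = 7.5 and 40/4 = 10, against 53.3/4 = 13.3.

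**B. Phase 3 rule: is the 360-event target itself sound?**

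Inputs: 450 participants randomized 1:1, medians of 11 and 15 days (Protocol 9.2), 30 days of follow-up (Protocol 9.4.6). Assume exponential recovery times and no deaths.

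- Recovered by Day 30, rNAPc2: 1 − 2^(−30/11) = 0.849; 225 × 0.849 = 191.0.
- Recovered by Day 30, heparin: 1 − 2^(−30/15) = 0.750; 225 × 0.750 = 168.75.
- Total: 359.8, which reproduces the plan's 360.
- Upsized case: 600 × 359.8/450 = 479.7, which reproduces 480.

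The target is consistent with the assumptions; only the direction of the shortfall rule is wrong.

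**C. How likely is a shortfall?**

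Because 360 is the expected count, the simulated chance of fewer than 360 events from 450 is 48% with no deaths. The documents give no death rate, so three rates of death before recovery by Day 30 are assumed, using an equal constant death hazard in both arms (0.0035, 0.0073 and 0.0114 per day).

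| Death before recovery (assumed) | Expected events from 450 | Chance of fewer than 360 | Randomized to expect 360 = 360 × 450/events |
|---|---|---|---|
| 0% | 359.8 | 48% | about 450 |
| 5% | 346.3 | 94% | 468 (+18) |
| 10% | 332.5 | over 99% | 488 (+38) |
| 15% | 318.4 | over 99% | 509 (+59) |

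**D. What does the rule protect?**

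Power was simulated with 20,000 trials per case, an unstratified log-rank test and two-sided alpha 0.0499; the Monte Carlo standard error is about 0.3 points. Participants who die stay in the risk set to Day 30, following the censoring rule in Protocol 9.4.2.

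| Death before recovery (assumed) | Power at 450 | Power with enough randomized to expect 360 events (N simulated) | Difference |
|---|---|---|---|
| 0% | 83.9% | – | – |
| 5% | 79.3% | 80.9% (468) | 1.6 |
| 10% | 75.2% | 79.1% (488) | 3.9 |
| 15% | 71.5% | 76.8% (510) | 5.3 |

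A repeat with 40,000 trials per case gave differences of 1.5, 3.4 and 5.0 points. For contrast, censoring at death with 450 participants gives 81.9, 80.8 and 79.5%. Much of the fall from 83.9% therefore comes from how deaths are handled, and the wording of this rule does not affect that part.

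**The case against.** **Both sentences can be used despite the slips.** The count of 30–40 can be applied on its own, and it is the earlier of the two looks, so following it delays nothing. In the Phase 3 sentence the stated purpose fixes the meaning, and Protocol 7.2 supports it. This is fair, and it limits the harm. It does not settle which safety trigger was meant, and a pre-specified sample-size rule should not have to be read against its own words.

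**Details sit in other documents.** Protocol 9.4.6 refers to an interim analysis plan for each phase. SAP Sections 1 and 4.1 refer to the DSMC Charter and a reporting plan, and Phase 3 is to have its own analysis plan. None of these is available here, and they may be clear. But they are described as adding detail, and for the safety look they would have to follow one half of the protocol sentence or the other.

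**The count may be a leftover.** The amendment log records a sample size increase in version 6.00, and 30–40 would be one third of 90–120. That is plausible, but the log does not give the old target, so it remains an inference.

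**Other safety review continues.** The Chairperson's monthly review, unscheduled meetings and the look at 120 participants are unaffected. This stands.

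**The power figures are hypothetical.** They need someone to apply the inverted rule literally, and they rest on assumed death rates and an unstratified test where the plan specifies a stratified one. A 48% chance of missing 360 is close to automatic when 360 is the expected count. Power has some slack: Schoenfeld's formula at HR 1.36 needs 333 events for 80% and gives 83.1% at 360, and the simulated 79.3% at 5% deaths still fits the plan's approximate 80%. All of this stands. The figures show what a working rule is worth, not a loss that will occur.

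**Conclusion.** Both errors are in the current text, and no other section of the protocol or SAP corrects them.

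For Phase 2b, the fraction and the count differ by 13 to 23 participants. The word *approximately* cannot cover this, since 53 is a third above the top of the stated range. This result needs no assumption beyond the documents' own target.

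For Phase 3, the condition is the reverse of its purpose. That follows from the wording alone. The size of the consequence depends on the assumptions above (exponential recovery, equal constant death hazards, assumed death rates of 5 to 15%): a rule that works is worth about 2 to 5 points of power and requires 18 to 59 more participants. With no deaths the plan still has about an even chance of falling short of 360, so the rule would probably come into play.

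These are drafting errors in operative decision rules. They should be corrected, but they do not undermine the design.

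**What to change.** In Protocol 9.4.6:

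- **Safety look.** State one trigger, with a fraction and a count that agree for a target of 160. One third corresponds to about 53 participants; 30–40 corresponds to roughly one fifth to one quarter. The sponsor must say which is intended and carry the same figure into the DSMC Charter and the Phase 2b interim analysis plan.
- **Phase 3 rule.** Change *unlikely* to *likely*, so that participants are added when fewer than 360 events, or fewer than the upsized target, are likely.

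The cost is one reconciled figure and one word. The adaptive rule, sample size and analysis stay as they are.

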9.4.7 SUBGROUP ANALYSES

For the primary efficacy endpoint for each Phase, the treatment effects across the following subgroup factors will be examined:

- D-dimer
- Gender
- Age group (<65, ≥65 years)
- Race/ethnicity
- Planned or ongoing therapy with an agent with demonstrated efficacy in patients with COVID-19 (yes, no)
- Baseline ACTT ordinal scale category
- Background antiplatelet therapy at baseline

For the Phase 2b primary efficacy endpoint, possible heterogeneity in the treatment effect for subgroups within each factor will be assessed by including the factor and the interaction between the factor and treatment in the analysis of covariance (ANCOVA) model.

Additionally, the heterogeneous application of heparin dichotomized by therapeutic vs. prophylactic uses, as well as the different standards of use across site, pose the need for sensitivity analyses to determine the degree to which the primary endpoint finding generalizes across sites.

Similarly, for the Phase 3 primary efficacy endpoint, possible heterogeneity in the treatment effect for subgroups within each factor will be assessed by including the factor and the interaction between the factor and treatment in the Cox proportional hazards model.

9.4.8 PHASE 2B TO 3 TRANSITION

At the end of the Phase 2b study, data will be analyzed, and a dose and comparator arm will be identified. The Phase 3 study will then resume once appropriate regulatory authority communications have been conducted and concluded.

10 SUPPORTING DOCUMENTATION AND OPERATIONAL CONSIDERATIONS

10.1 REGULATORY, ETHICAL, AND STUDY OVERSIGHT CONSIDERATIONS

10.1.1 INFORMED CONSENT PROCESS

10.1.1.1 CONSENT AND OTHER INFORMATIONAL DOCUMENTS PROVIDED TO PARTICIPANTS

Each participant or their Legally Authorized Representative (LAR) must provide electronic or written informed consent according to local requirements after the nature of the study has been fully explained.

A LAR is defined by the US Department of Health and Human Services as “any individual person, judicial body or other body of individuals who are legally authorized under state and federal law to consent to research participation on behalf of a designated person.” The LAR may be a parent, grandparent, or caregiver who has the legal authority to grant consent on behalf of another who has been invited to participate in research.

The ICF must be signed before performance of any study-related activity. The ICF and any other written information provided to participants must be approved by both the sponsor and by the reviewing IEC/IRB and be in a language that the participant can read and understand. The consent should be in accordance with principles that originated in the Declaration of Helsinki, current International Conference on Harmonisation (ICH) and GCP guidelines, applicable regulatory requirements, and sponsor policy.

10.1.1.2 CONSENT PROCEDURES AND DOCUMENTATION

Before enrollment in the study, the investigator or an authorized member of the study-site personnel must explain (in a language the participant understands) to potential participants or their LAR the aims, methods, reasonably anticipated benefits, and potential hazards of the study, and any discomfort participation in the study may entail. Participants will be informed that their participation is voluntary and that they may withdraw consent to participate at any time. They will be informed that choosing not to participate will not affect the care the participant will receive. Participants will be told that refusal to take part in the study will not prejudice future treatment. Finally, they will be told that the investigator will maintain a participant identification register for the purposes of long-term follow-up if needed and that their records may be accessed by health authorities and authorized sponsor personnel without violating the confidentiality of the participant, to the extent permitted by the applicable law(s) or regulations. By signing the ICF, the participant or LAR is authorizing such access, which includes permission to obtain information about his or her survival status.

The participant or LAR will be given sufficient time to read the electronic ICF and the opportunity to ask questions. Once the participant or LAR understands all aspects of the ICF, consent should be appropriately recorded by means of the participant’s or LAR’s signature. After having obtained the consent, the participant will receive a signed/dated copy for their records.

If the participant or LAR is unable to read or write, an impartial witness should be present for the entire informed consent process (which includes reading and explaining all written information) and should personally date and sign the ICF after the oral consent of the participant [or LAR] is obtained.

The ICF and any other written information provided to participants will be revised whenever important new information becomes available that may be relevant to their consent, or there is an amendment to the protocol that necessitates a change to the content of the patient information and/or ICF. The investigator will inform the participant or their LAR of changes in a timely manner and will ask the participant or their LAR to confirm his/her participation in the study by signing the revised ICF. Any revised written ICF and written information must receive the IEC/IRB’s approval/favorable opinion in advance of use.

Informed consent for study participation includes collection and storage of plasma and serum samples for future research on sequelae of COVID-19. Separate consent will be requested for collection and analysis of Deoxyribonucleic acid (DNA) for future research on genetics of COVID-19 sequelae and

response to treatment. Participants may join the study without agreeing to collection and analysis of DNA.

